2.2 Secondary Aims

2.2.1. The **secondary aim** of this proposal is to assess the effect that administration of pancreatic enzymes will have on global absorption. Specifically, CNA and stool BC will be measured to detect changes in enteral protein absorption and stool energy losses, respectively, before and after administration of pancreatic enzymes.

We hope to address the unique difficulty of measuring enteral fat absorption in subjects with SBS. Fat absorption in a subset of subjects will be measured using the MBT. CCK concentration will also be measured in this subset as an additional area of exploration, as CCK plays a pivotal role in pancreatic enzyme secretion⁶. Additionally, we hope to explore the effect that improved nutrient absorption will have on intestinal adaptation by measuring markers of intestinal mass and hormone levels.

2.2.2. We will **explore** the ability of the MBT to detect changes in enteral fat absorption before and after administration of pancreatic enzymes in a subset of patients. This test will also help characterize the degree of pancreatic insufficiency in subjects. Baseline serum CCK concentration and serum CCK concentration following pancreatic enzyme therapy will also be determined in this subset.

2.2.3 A final aim will **explore** if improved lipid digestion and release of free fatty acids due to pancreatic enzymes will promote intestinal adaptation by stimulating endocrine signaling. Specifically, GLP-2, IGF-1, IGFBP-3, and GH concentrations will be measured from blood samples before and after administration of pancreatic enzymes. Plasma citrulline will also be measured as a marker of intestinal adaptation before and after administration of pancreatic enzymes.

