6.3.1 Efficacy Analysis

Statistical Analysis: **H1, H2, and H3:** Descriptive statistics for CFA, CNA, and BC outcomes (mean, standard deviation, median, range, 95% CI) will be calculated for the SBS cohort before and after PERT administration with paired t-tests or Wilcoxon sign rank tests depending on skewness of data. For the MBT outcomes, a moment-based pharmacokinetic (PK) analysis will be performed based on non-compartmental methodology using WinNonLin version 9.1 (Pharsight, Cary, NC). Baseline (C_0) and maximum (C_{max}) plasma concentrations are calculated, and area under the curve from time zero to eight hours (AUC) is calculated using the linear trapezoid method. PK parameters can then be compared between treatment groups using a paired t-test or Wilcoxon signed rank test as appropriate. To describe HA exposure relative to that of PA, the ratio of the HA to PA C_{max} (C_{max} HA/PA) and AUC (AUC HA/PA) is calculated for each subject after molar transformation and dose-normalization of exposure metrics⁷. Alternately, population PK analyses for repeated-measures endpoints can be conducted via nonlinear mixed-effects modeling with a qualified installation of the nonlinear mixed-effects modeling (NONMEM) software, Version VII, Level 2.0 (ICON

Development Solutions, Hanover, MD⁸. Using this method, population PK modeling is conducted by simultaneously fitting structural PK models to both PA and HA concentrations⁹.

In exploratory analyses, we will compare the estimates of percent fat absorption from the MBT with both the CFA% from the 72-hour fecal fat and diet analysis and the BC results (energy loss in the stool). We will compare the methods for detection of fat malabsorption as measured by CFA% and BC with fat absorption as measured by MBT for the subjects before and after pancreatic enzyme medication use. A correlation analysis will be conducted to evaluate the performance of the MBT relative to that of the CFA%. HA and PA C_{max}, AUC, and HA/PA ratios will be plotted against CFA% or BC caloric loss to explore the relationship between the two tests. Any relationships observed in the plots will be further explored using correlation analysis and appropriate regression analysis as dictated by the observations.

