Assessment of fat malabsorption using the MBT method (**H3**) will be conducted on a subset of 10 subjects and is exploratory. We have previous experience in CF and PI with detecting differences in the pharmacokinetic parameters C_{max} and AUC for HA and the HA/PA ratio⁷, and in detecting the percent change in HA absorption (from pharmacokinetic modeling) compared to healthy subjects⁹, and in detecting changes in subjects with CF before and after pancreatic enzyme administration^{7,9}. We have demonstrated differences in the magnitude of MBT outcomes (exposure metrics) indicating the degree of fat absorption in these subjects with varying treatment regimens of approximately 0.5 in both C_{max} and AUC HA/PA ratios with a standard deviation of ~ 0.7 . Differences of this magnitude were significant with samples of 16 subjects or less. Given the small sample size of this subset of subjects with SBS (n=10) and the known moderate variability within subjects in PA and HA with CF and PI^{7,9}, the use of the MBT method to detect fat malabsorption in SBS is considered an exploratory aim, and will inform future studies once effect sizes in the MBT outcomes are determined.

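### The MBT is judged against CFA% by correlation alone, which shows neither agreement between the two nor whether a subject's MBT change tracks the CFA change

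*Combined protocol and SAP*

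**What the plan says.** Section 2.2 (aim 2.2.2) sets out to explore "the ability of the MBT to detect changes in enteral fat absorption before and after administration of pancreatic enzymes", and adds that the test will help describe how pancreatic-insufficient the subjects are. Section 6.4 says that the MBT assessment "will be conducted on a subset of 10 subjects and is exploratory".

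Section 6.3.1 Efficacy Analysis has two separate strands.

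- The MBT's own change: "PK parameters can then be compared between treatment groups using a paired t-test or Wilcoxon signed rank test as appropriate".
- The MBT against stool measures: "we will compare the estimates of percent fat absorption from the MBT with both the CFA" and with bomb calorimetry (BC). The comparison concerns "fat absorption as measured by MBT for the subjects before and after pancreatic enzyme medication use". Performance is to be judged as follows: "A correlation analysis will be conducted to evaluate the performance of the MBT relative to that of the CFA". For the plots, Cmax, AUC and "HA/PA ratios will be plotted against CFA% or BC caloric loss to explore the relationship between the two tests". Anything seen there leads to "correlation analysis and appropriate regression analysis as dictated by the observations".

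The second strand names no measure of agreement, does not mention relating change to change, and does not say how two observations per subject are handled.

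**The concern.** Section 1.5 treats CFA as the reference standard for gut absorption and notes how hard absorption is to measure in short bowel syndrome. The MBT is therefore of interest as another way to measure it. Two questions matter for that use: does MBT percent absorption give about the same figure as CFA%, and does a subject's MBT response to enzyme reflect that subject's CFA response?

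A correlation of levels answers neither. It ignores constant and proportional bias, and it is driven largely by how much subjects differ from one another at any one time. A high value could be reported as good MBT performance although the test is badly biased or its changes carry no information about CFA change. A lesser issue is that each subject contributes two points and the plan does not exclude analysing them as independent.

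**Working it through.** **Inputs from the documents.** At most 10 MBT subjects (6.4), with the option to decline (5.2.2), and two MBTs each, so up to 20 points. CFA change 9 with SD of differences 14, two-sided alpha 0.05 (6.4). HA/PA ratio difference about 0.5 with SD about 0.7 (6.4).

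**Assumption.** The within-subject correlation between periods, rho, is not given; I use 0 to 0.9 for both measures.

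**1. The plan's own figure.** No figure is stated for the MBT-CFA correlation. The nearest is 80% power for CFA with 22 subjects. The noncentrality is 9/14 × √22 = 3.015, and exact paired-t power is 0.820. It reproduces (21 subjects suffice for 80%).

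**2. Agreement (illustration).** Let MBT% = 0.5 × CFA% + 10, at CFA 50, 60, 70, 80 and 90.
- Means are 70 and 45, so the mean difference is -25 points.
- Variances are 200 and 50, covariance 100, so r = 100/√(200 × 50) = 1.00.
- Concordance coefficient = 2 × 100/(200 + 50 + 25²) = 200/875 = 0.23.

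**3. Tracking of change (illustration).** Each measure is √rho × subject effect + √(1 − rho) × visit error. The subject effects of the two measures correlate 0.9, the visit errors are independent, and rho is 0.7. The expected correlation of levels within one period is 0.9 × 0.7 = 0.63. In a change score the subject effect cancels, so the change correlation is 0. Simulation with 10 subjects:

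| Statistic | Mean r | Significant at 5% |
|---|---|---|
| Levels, both periods pooled | 0.59 | 81% |
| Levels, one period | 0.61 | 54% |
| Change on change | 0.00 | 5% |

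Splitting by period does not cure this, because a level correlation is simply not about change.

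**4. Pooling, if it were done.** There is no true association, 10 subjects, and 20 points treated as independent. The critical |r| falls from 0.632 (n = 10) to 0.444 (n = 20). The second row adds mean shifts of 9/14 = 0.64 SD for CFA and 0.5/0.7 = 0.71 SD for HA/PA.

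| rho | 0 | 0.3 | 0.5 | 0.7 | 0.8 | 0.9 |
|---|---|---|---|---|---|---|
| Rejection, no shift | 5.0% | 5.9% | 7.9% | 11.3% | 13.6% | 16.6% |
| Rejection, plan's shifts | 7.2% | 7.6% | 8.9% | 11.5% | 13.3% | 15.2% |

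Single-period and change-score correlations stay at about 5% throughout. The second row uses 14 and 0.7 as SDs of levels, although 6.4 gives 14 as an SD of differences; the two coincide at rho = 0.5. With both used as SDs of differences instead, the row runs from about 9% to 15%.

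**5. Precision at n = 10.** Fisher interval: atanh(r) ± 1.96/√7. For r = 0.6 this is 0.693 ± 0.741, so the 95% CI is -0.05 to 0.89. Each limit of agreement has a CI half-width of about 2.262 × √(1/10 + 1.96²/18) = 1.27 SDs of the differences.

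**The case against.** The strongest reply is that aim 2.2.2 is already served. A reader might infer that the plan never tests whether the MBT detects change. The documents do not support that: 6.3.1 specifies paired tests on the PK parameters, and 5.2.2 defines the MBT outcomes as comparisons before and after enzyme. What is missing is narrower: whether MBT change follows CFA change.

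A reader might also infer that both periods will be pooled as 20 independent points. The text does not say so. It fits separate analyses equally well, states no alpha for this correlation, and leaves room for a suitable regression. Change scores are not excluded either; that levels are meant is inferred from the quantities plotted. The rejection rates in step 4 therefore describe a hazard left open. Larger rates need treatment shifts bigger than the plan's figures imply, and nothing in the documents supports such shifts.

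Two further points stand. Level correlations are legitimate for the other half of aim 2.2.2, the degree of insufficiency, so they should not be removed. Agreement statistics need a common scale; Cmax, AUC, HA/PA and BC do not share one with CFA%, and for them association is the feasible measure.

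Finally, the work is exploratory. That limits the severity, but it does not make correlation informative about agreement or tracking.

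**Conclusion.** The point holds as a modest improvement to an exploratory analysis. Correlation is the only statistic named for judging the MBT against CFA%. It can be 1.00 with a bias of 25 points, and it can average about 0.6 when changes are unrelated. Both are illustrations with assumed values, not predictions for this trial.

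The pooling issue is conditional on a step the plan does not state. Its size, about 5% to 17% without a shift and about 7% to 15% with the plan's shifts, rests on an assumed within-subject correlation of 0 to 0.9. With no shift it vanishes at a correlation of 0. The paired tests of MBT change and the primary CFA analysis are not affected.

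**What to change.** In 6.3.1 Efficacy Analysis:

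- Keep the level correlations, but compute them separately before and after enzyme. If the periods are combined, use repeated-measures correlation.
- Add the correlation of within-subject change in the MBT (HA/PA AUC ratio and percent absorption) with change in CFA%, with its 95% CI.
- Add the mean difference and Bland-Altman limits of agreement, by period, for MBT percent absorption against CFA% only.
- Report all of these as exploratory estimates with confidence intervals.

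The cost is wording and a little programming, on measurements already planned. The price is imprecision: with 10 or fewer pairs the intervals will be wide. Limits of agreement also need cautious reading, because the MBT reflects one test meal and CFA% reflects usual diet with a 72-hour stool collection, so some disagreement is expected even if both are accurate.

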6.3.1 Safety Analysis

Safety will be monitored by adverse events reporting. The frequencies of AEs by type, body system, severity and relationship to study supplement will be summarized. SAEs (if any) will be described in detail.

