- Those subjects who are on a medication that directly alters fat absorption will discontinue this medication after permission is obtained from their primary gastroenterologist. Study team must have a signed, informed consent form prior to discontinuation of medication.
- Subject's normal diet

Day 8 – CHOP Visit to CTRC Outpatient Lab and NGL

- Sign informed consent form if study visit 0 conducted via telephone for those subjects who do not have to discontinue medication or have labs at study visit 0
- 24-hour dietary recall for those subjects who sign the informed consent form at study visit 1
- Urine pregnancy test for pre-menopausal females
- Subject's normal diet
- Baseline blood draw: Fat soluble vitamins (A, D, E, K)*, pre-albumin, serum zinc*, selenium*, fatty acid profile*, citrulline, IGF-1, IGF BP3, GLP-2, GH, CBC, CMP, hepatic function panel
- Anthropometry (height, weight, skinfolds, circumferences)
- Whole body DXA

- Spot stool sample will be collected for stool pH and fecal elastase. Subjects who are unable to produce a sample at the visit will collect and freeze a stool sample at home on one occasion on Day 8, 9, or 10.
- If subject has a G tube, spot gastric pH will be checked
- Questionnaires: Health History and medications, Home Environment, Quality of Life (MOS SF-36 or PedsQL)
- Instructions will be given for collection and shipping for: stool collection (72-hour fecal fat and nitrogen analysis and bomb calorimetry), 3-day weighed food records, and adverse events diary
- Prescribe Creon™ and dispense to subjects

Day 9 - Home

- Maintain adverse events diary
- Subject's normal diet

Day 10 - Home

- Subject's normal diet
- 3-day weighed food record begins
- Food record – Day 1
- Maintain adverse events diary

Day 11 - Home

- Subject's normal diet
- Food record – Day 2
- Stool collection begins (72-hour fecal fat, 72-hour fecal nitrogen, and bomb calorimetry), store frozen until brought to CHOP.
- 72-hour stool – Day 1
- Maintain adverse events diary

Day 12 - Home

- Subject's normal diet
- Food record – Day 3
- 72-hour stool – Day 2
- Maintain adverse events diary

Day 13 - Home

- Subject's normal diet
- 72-hour stool – Day 3
- Maintain adverse events diary

- These laboratories will be drawn at study visit 0 if the subject weighs less than 25 kg

Study Visit #1: Protocol for non-MBT/CCK Subjects who are Receiving Pancreatic Enzyme Medication Prior to Study Visit # 1 and require a Washout Period

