4.4 Open-Label Treatment with Creon™

Subjects will receive open-label treatment with Creon™ as their pancreatic enzyme medication therapy and will receive this therapy for nine days encompassing Study Visit #2. There are two protocols for Study Visit #2. The first protocol is for subjects in the non-MBT/CCK cohort and the second protocol is for subjects in the MBT/CCK cohort. Please note that subjects who are eligible for the MBT/CCK subset and decline the MBT will follow the same protocol as the non-MBT/CCK subset.

Study Visit #2: Pancreatic Enzyme Medication Treatment Protocol for Subjects in the non-MBT/CCK Subset

Days 1 -4

- Pancreatic enzyme medication treatment
- Subject's normal diet

Day 5 – CHOP Visit to CTRC Outpatient Lab and NGL

- Subject's normal diet
- Pancreatic enzyme medication treatment

- Blood draw: pre-albumin, citrulline, IGF-1, IGF BP3, GLP-2, GH, CBC, CMP, hepatic function panel
- Spot stool sample will be collected for stool pH
- If subject has a G tube, spot gastric pH will be checked
- Adherence to pancreatic enzyme medication and Adverse Events Questionnaires
- Instructions will be given for collection and shipping for: stool collection (72-hour fecal fat, 72-hour fecal nitrogen, and bomb calorimetry), 3-day weighed food records, and adverse events diary

Day 6 - Home

- Pancreatic enzyme medication treatment
- Subject's normal diet
- Maintain adverse events diary

Day 7 - Home

- Pancreatic enzyme medication treatment
- Subject's normal diet
- 3-day weighed food records begins
- Food record – Day 1
- Maintain adverse events diary

Day 8 - Home

- Pancreatic enzyme medication treatment
- Subject's normal diet
- Food record – Day 2
- Stool collection (72-hour fecal fat, 72-hour fecal nitrogen, and bomb calorimetry), store frozen until brought to CHOP.
- 72-hour stool – Day 1
- Maintain adverse events diary

Day 9 - Home

- Pancreatic enzyme medication treatment
- Subject's normal diet
- Food record – Day 3
- 72-hour stool – Day 2
- Maintain adverse events diary

Day 10 - Home

- Pancreatic enzyme medication treatment

- Subject's normal diet
- 72-hour stool – Day 3
- Maintain adverse events diary

Day 11 - Home

- Subjects who had discontinued a medication that directly alters fat absorption for this study can resume this medication as it was prescribed by their primary physician

Study Visit #2: Pancreatic Enzyme Medication Treatment Protocol for Subjects in the MBT/CCK Subset

Days 1, 2, & 3

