Home Environment and Health Questionnaire: The questionnaire will be administered via interview by the research staff at Study Visit #1, and will consist of two sections. The Health History section has general questions about the subject's health history including documentation of medical history, recent hospital admissions and illnesses, medication, history of pancreatic enzyme supplementation, parenteral nutrition, and nutrient supplement use. A Home Environment section describes aspects of environment, such as education and income level, whether on Medicaid/Medicare and household size to describe the demographic characteristics. In addition to subjects' contact information (name, address, phone numbers); contact information from two additional contacts will be collected to maintain contact with the subject in the event that the subject cannot be contacted at their primary residence.

Quality of Life Questionnaires: In order to assess the health-related quality of life (QOL), validated questionnaires will be administered to all subjects at Study Visit #1. For all subjects 18 years of age and older, the Medical Outcomes Study 36-Item Short-Form Health Survey (MOS SF-36), a standardized, validated health survey will be administered. The MOS SF-36 covers physical functioning, bodily pain, general health perception, vitality, social functioning, emotional and mental health domain²⁵. For subjects between 4 and 17.9 years of age, the Pediatric Quality of Life Inventory (PedsQLTM) is a validated health survey that will be administered. For subjects who are 4 years old, a parent or legal guardian only will complete a proxy-report. For subjects between the ages of 5 and 17.9, both the subject and the parent or legal guardian will complete a survey. The PedsQLTM addresses physical, emotional, social, and school functioning²⁶.

Adherence: Adherence to pancreatic enzyme medication for subjects will be assessed at Study Visit #2 and #3 and by phone calls. This time will also be used to trouble-shoot any barriers to adherence, and also to collect information on adverse events experienced during the course of the study.

Adverse Events Diary: Subjects will be asked about all adverse events at Study Visit #1, Study Visit #2, and Study Visit #3 and asked to rate by intensity (mild, moderate, severe). Serious adverse events will be reported as per various policies in a timely manner to CHOP IRB, and CTRC.

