* Will not exceed maximum daily enzyme dosing of 10,000 lipase units/kg/day

⁺ The dose of enzymes with each bolus depends on the enteral feeding regimen, grams of fat, and the volume and number of boluses

Bolus feeds: The dose of enzymes that each subject receives prior to each bolus will depend on the volume and total number of boluses received per day. We will attempt to cover each bolus with a maximum dose of 1500 – 2500 lipase units/kg/meal, but this may be reduced if boluses are smaller in volume or occur frequently.

Overnight feeds: This group includes subjects on overnight enteral feeds for 8-12 hours. These subjects will receive one meal dose of Creon™ (1500 - 2500 lipase units/kg) prior to feeds and one meal dose of Creon™ at the end of feeds, consistent with our current practice at CHOP.

Continuous feeds: This group includes those subjects on continuous enteral feeds for 20-24 hours of the day. For these subjects, we will dose enzymes every 4 hours while awake based on grams of fat in the formula and based on recommended dosing per grams of fat. Overnight, they will receive one meal dose of Creon™ (1500 – 2500 lipase units/kg) before and after the overnight feed.

We will not exceed 10,000 lipase units/kg/day or 4000 lipase units/grams of fat/day for any subject¹³. Each subject will receive pancreatic enzyme medication for a total of ten days. They will start Creon™ 4 days prior to study visit #2, they day of study visit #2, and then for five days after the visit until they have completed the second stool collection.

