9.4.2 Risk Assessment

The most common side effects associated with taking the pancreatic enzyme Creon™ in clinical trials were abdominal pain, hyperglycemia, hypoglycemia, frequent abnormal bowel movements, flatulence, vomiting, dizziness, sore throat and cough. Irritation of the inside of the mouth may occur if Creon™ is not swallowed completely. Additionally, subjects in diapers are at risk of diaper dermatitis due to Creon™ if diapers are not changed frequently and a heavy barrier cream is not utilized. Increase in blood uric acid levels (hyperuricemia), and severe allergic reactions (pork allergy) including trouble with breathing, skin rashes or swollen lips, although rare, may occur. Although it has never been reported, it is possible for a person to get a viral infection from taking pancreatic enzyme products that come from pigs. Fibrosing colonopathy and colonic strictures is a rare, serious adverse reaction associated with chronic high-dose pancreatic enzyme use over a prolonged period of time with enzyme doses in excess of 6,000 LU/kg body weight per meal or 10,000 LU/kg/day in patients with cystic fibrosis. Doses of Creon™ prescribed for this study will not exceed 10,000 LU/kg/day or 4000 LU/grams of fat/day for any subject.

There are risks associated with discontinuing pancreatic enzyme medication for subjects with SBS who have noted clinical improvement on pancreatic enzymes. These include feelings of indigestion, stomach cramping after meals, gas, foul smelling, floating stools, light-colored, orange or yellow stools, frequent or loose stools, or weight loss. Some participants in the study may be at increased risk for these symptoms.

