- The participants receiving pancreatic enzyme medication prior to enrolling in the study who will discontinue use prior to the first study visit (Study Visit #1) may be at risk for signs and symptoms of fat malabsorption (described above) for nine days of the study. These nine days include the three days prior to Study Visit #1 (washout period), the day of Study Visit #1 to CHOP, and the five days of specimen collection after Study Visit #1. These participants will resume their pancreatic enzyme product and dose for the period of time between the end of the nine days encompassing Study Visit #1 and the start of the three days prior to Study Visit #2 when they will switch to Creon™ at doses prescribed based on the study protocol. Therefore, they will not be at increased risk for the signs and symptoms of fat malabsorption during the time between visits or during the ten days encompassing Study Visit #2 as they will be taking pancreatic enzyme medication throughout this period. When the study is completed, these participants will discontinue Creon™ and resume their usual care and resume their usual pancreatic enzyme product and dose.
- The participants who are naïve to pancreatic enzyme medication prior to entering the study, will take Creon™ for the ten days encompassing Study Visit #2 of the study, that is, four days prior to the protocol visit to CHOP, the day of the visit, and then five days after the visit until all specimen collections have been completed. If these participants have undiagnosed reduced pancreatic function and reduced fat absorption, they may have increased risk for the signs and symptoms of fat malabsorption upon discontinuation of

Creon™ at the end of the study. If their pancreatic function and fat absorption is normal, withdrawal from Creon™ at the end of the study will not increase their risk for these symptoms.

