Approximately ten adult subjects with SBS will have the option to have the MBT at both Study Visit #1 and Study Visit #2. During this test, a high fat supplement will be administered enterally. Subjects with poor absorption are therefore at risk of developing indigestion, abdominal pain or cramping, increased flatus, and frequent or loose stools. Ostomy output and stool output may increase and if estimated to be greater than 50 milliliters/kilogram/day, subjects may require serum electrolyte monitoring. If dehydration or severe electrolyte abnormalities occur, mainly acidosis (serum bicarbonate level less than 20 mmol/L) or hypokalemia (serum potassium less than 3.5 mmol/L), subjects will be hospitalized. Subjects who are primarily followed at The Children's Hospital of Philadelphia by [name], subjects less than 18 years, or subjects followed by pediatric gastroenterologists will be admitted to CHOP for monitoring, hydration, and electrolyte repletion. Subjects who are primarily followed at adult institutions will be discussed with [name]. [name] will assume their care and they will be hospitalized at the Hospital of the University of Pennsylvania.

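### The adverse-event tables have no split by study period, so off-enzyme and on-Creon events are told apart only by an open-label relatedness judgement

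*Combined protocol and SAP*

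**What the plan says.** Section 6.3.1 Safety Analysis gives the plan in one sentence, "The frequencies of AEs by type, body system, severity and relationship to study supplement will be summarized", and adds that serious events will be described in detail. Section 5.3 and the synopsis repeat it. No section defines a treatment-emergent event or assigns events to washout, off-enzyme baseline, Creon or follow-up.

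Collection covers all of these states. Section 5.1.3 says "Subjects will be asked about all adverse events at Study Visit #1, Study Visit #2, and Study Visit #3"; these visits fall off enzyme, on Creon and after Creon. Section 4.2 tells subjects "Maintain adverse events diary" on baseline Days 9 to 13, before Creon starts, and section 4.4 does the same on Creon Days 6 to 10. Section 8.3 records date and time of onset, and causality, for every event. Section 8.4.1 rates each serious event against the study activities as a whole.

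Section 9.4.2 names three sources of symptoms. One is Creon itself. The second is withdrawal: "There are risks associated with discontinuing pancreatic enzyme medication for subjects with SBS who have noted clinical improvement on pancreatic enzymes". The third is the high-fat MBT meal: "Subjects with poor absorption are therefore at risk of developing indigestion, abdominal pain or cramping, increased flatus, and frequent or loose stools".

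The term *study supplement* is not defined. Section 7 calls Creon the study medication, while section 9.4.2 calls the MBT shake a high-fat supplement.

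**The concern.** Abdominal pain or cramping, gas, and frequent or loose stools are expected from all three sources. A count of events by type and body system therefore says little about Creon unless it also shows what the subject was exposed to at onset. The plan's one means of separation is relationship to the supplement. That is an open-label judgement between similar-looking causes, made against a term that could mean either Creon or the shake.

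Sections 1.4 and 7.1.3 say that enzymes have not been studied in short bowel syndrome and state a preference for the highest doses deemed safe. Tolerability is therefore one of the main things this trial can report. Efficacy is compared within subject, before against after; safety is not, although the same off-enzyme period exists for it. Withdrawal of current enzymes is a risk that the study itself imposes, yet non-serious withdrawal events have no category of their own.

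**Working it through.** The plan attaches no event rate or count to the safety summary, so it has no figure to reproduce. Two checks apply.

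**1. How much scheduled observation is off Creon**

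Inputs:
- Enzyme-naive subjects, off enzyme: Visit 1 plus five days (section 4.2, Days 8 to 13) = 6 days.
- Prior users, off enzyme: three washout days, the visit day and five collection days = 9 days. Section 9.4.2 says they "may be at risk for signs and symptoms of fat malabsorption (described above) for nine days of the study".
- Creon: section 7.1.3 says "Each subject will receive pancreatic enzyme medication for a total of ten days" (4 + 1 + 5). Section 4.4 opens by saying that subjects "will receive this therapy for nine days encompassing Study Visit #2", although its own day list runs to Day 10.

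Share off Creon = off / (off + on):

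| Group | Creon 10 days | Creon 9 days |
|---|---|---|
| Naive | 6/16 = 37.5% | 6/15 = 40% |
| Prior users | 9/19 = 47.4% | 9/18 = 50% |

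The count leaves out Visit 3 and any interval between the first stool collection and the start of Creon, because their length is not fixed.

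**2. What this could do to a combined count**

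The documents give no background rate. Assume that a fraction p of subjects has at least one gastrointestinal event in ten days from background alone, that the daily rate is constant, that Creon adds nothing, and that the periods are independent. The combined fraction over D days is 1 − (1 − p)^(D/10), with D = 16 for naive subjects and D = 19 for prior users.

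| p over 10 Creon days | Naive, 16 days | Prior users, 19 days |
|---|---|---|
| 20% | 1 − 0.8^1.6 = 30% | 1 − 0.8^1.9 = 35% |
| 30% | 1 − 0.7^1.6 = 43% | 1 − 0.7^1.9 = 49% |
| 40% | 1 − 0.6^1.6 = 56% | 1 − 0.6^1.9 = 62% |

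At p = 30% and 26 subjects, the Creon period alone gives 0.30 × 26 = 7.8 subjects with an event. The combined count gives 0.435 × 26 = 11.3 if all are naive and 0.492 × 26 = 12.8 if all are prior users. The number of prior users is not stated, so the mix lies between these.

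Independence is the unfavourable end. If the same subjects have symptoms in both periods, which chronic disease makes plausible, the combined figure falls towards p itself, 30%. The range at p = 30% is therefore 30% to 43% (naive) or 30% to 49% (prior users).

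**The case against.** The strongest reply is that the plan is silent on periods rather than wrong about them. It never says that events will be pooled, and the recorded onset dates allow a split at analysis. A reader might infer that the protocol requires a pooled table from which Creon's effect can never be recovered; the documents do not support that. What stands is that the split is not planned, and a split chosen after the data are seen, in an open-label study, carries less weight than one written now.

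The plan also does not ignore causes other than the supplement. Serious events are rated against study activities and narrated. The gravest MBT harm that section 9.4.2 foresees, hospitalisation for dehydration or electrolyte disturbance, would be a serious event under section 8.4. The gap is in the non-serious table.

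The symptom lists overlap but are not identical. Creon's also includes glucose disturbance, dizziness, sore throat and cough, which the planned breakdown by type and body system would show separately.

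On size, a reader might give every subject two equal windows and obtain 1 − 0.7² = 51% at p = 30%. The schedule does not support this, because the off-enzyme period is 6 or 9 days against ten on Creon, and independence is itself an assumption. The combined figures are also all-causality counts, not counts of events judged related to Creon.

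Finally, a within-subject on-versus-off comparison cannot establish that Creon adds or removes symptoms. The order is fixed, treatment is open-label, and for prior users the off period is a withdrawal state. The two diary windows also miss the washout days, both visit days and early Creon. All of this stands, and it limits the comparison to description.

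**Conclusion.** The point holds as a gap in the descriptive safety analysis that should be closed. The planned table mixes exposure states and leaves their separation, for non-serious events, to an unblinded rating against an undefined term. That between 37.5% and 47.4% of scheduled days before and on Creon are off Creon (40% and 50% on the nine-day text) follows from the schedule alone. The rise from 30% to 43–49% is an illustration resting on an assumed background risk, a constant daily rate and independent periods; the true excess could be close to nil if symptoms recur in the same subjects. Whatever its size, a table without periods cannot show how much of the total arose off Creon. The analysis of the coefficient of fat absorption is not touched.

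**What to change.** In sections 5.3 and 6.3.1 Safety Analysis, and in the synopsis:

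- Tabulate events by onset period (off enzyme including washout, on Creon, after Creon), with days observed in each, separately for enzyme-naive subjects and prior users. State where events between the first collection and the start of Creon belong; section 9.4.2 has prior users back on their own product then.
- Report the within-subject difference in gastrointestinal events over the matching five-day diary windows (baseline Days 9 to 13, Creon Days 6 to 10), labelled descriptive.
- List events on washout days, visit days and Creon Days 1 to 5 separately, because no diary is scheduled then and ascertainment differs.
- Replace *study supplement* with separate attributions to Creon, enzyme withdrawal and the MBT meal. The period split alone will not isolate the meal, because the second MBT is given on Creon.
- Reconcile the texts that define the periods. Creon lasts ten days in sections 7.1.3 and 9.4.2 but nine in the opening of section 4.4. It starts four days before Visit 2 in sections 3.1.3 and 7.1.3, but one paragraph of section 9.4.2 says three, and Tables 3 and 4 put Visit 2 on the fourth treatment day.

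The cost is one extra table, a few sentences and one added attribution item per event on the case report form. Onset dates are already collected; the attribution is a new judgement for each event.
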